h. Schedule of events	45
i. WMA Declaration of Helsinki - Ethical Principles for Medical Research Involving Human Subjects.....	46
i. Preamble.....	46
ii. General Principals	46
iii. Risks, Burdens and Benefits.....	47
iv. Vulnerable Groups and Individuals.....	48
v. Scientific Requirements and Research Protocols	48
vi. Research Ethics Committees	49
vii. Privacy and Confidentiality	49
viii. Informed Consent.....	49
ix. Use of Placebo.....	50
x. Post-Trial Provisions.....	51
xi. Research Registration and Publication and Dissemination of Results	51
xii. Unproven Interventions in Clinical Practice	51

1. Summary

Title:	Efficacy of Near Infrared Incisionless Fluorescent Cholangiography (NIFC) during Laparoscopic Cholecystectomy (LC)
Primary Objective:	Demonstrate that NIFC performs better than standard white light (WLI) alone in visualizing and identifying extra-hepatobiliary structures (Cystic Duct, Right Hepatic Duct, Common Hepatic Duct, Common Bile Duct, Cystic-CBD junction, Cystic-Gallbladder junction, and any Accessory Ducts) before and after dissection during Laparoscopic Cholecystectomy (LC).
Secondary Objectives:	
1. Demonstrate that NIFC is an effective teaching tool to assist students and residents present in the O.R. during the procedure to identify extra-hepatobiliary structures (before/after dissection).2. Demonstrate that the Time to Clip, which is defined as the time from the moment Calot's Triangle is first visualized to when the clip is applied, is reduced when using NIFC vs WLI alone.3. Compare the mean number of procedures that required Conversion to Open using NIFC vs WLI alone.4. Compare the mean Volume of Bleeding using NIFC vs WLI alone.5. Compare the Incidence rate of Bile Leakage from the liver bed using NIFC vs WLI alone.6. Compare the Incidence rate of Bile Duct Injury (BDI) using NIFC vs WLI alone.7. Compare the mean Surgeon Confidence Level using NIFC vs WLI alone.
Indication:	Laparoscopic Cholecystectomy (LC)
Investigational Design:	Two arms multi-center randomized controlled clinical trial with patients randomized by center.
Inclusion/exclusion criteria:	
Inclusion Criteria
 
1. Patients of both genders2. Minimum age: 18 years old3. Spoken and written command of the language spoken in the country's center

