	
4. Ability to understand and follow the study procedures and sign the informed consent
 
Exclusion Criteria
 
1. Known allergies to iodides2. Known history of cholangitis, pancreatitis, CBDS's, coagulopathy3. Known liver disease4. Women who are pregnant or breastfeeding, or for whom possibility of pregnancy was not ruled out 
1,000 patients enrolled across all centers
 
Male or female subjects undergoing laparoscopic cholecystectomy that fulfil all of the inclusion and none of the exclusion criteria.
 
Approximately 1 year
 
Primary Endpoints:
 
Detection Rate (DR) of each particular extra-hepatobiliary structure during Laparoscopic Cholecystectomy (LC) defined as the total number of patients in which the particular structure is detected before and after dissection in that arm of the Study (WLI or NIFC), divided by the total number of patients in that arm. Extra-hepatobiliary structures to be included in this assessment: Cystic Duct, Right Hepatic Duct, Common Hepatic Duct, Common Bile Duct, Cystic-CBD junction, Cystic-Gallbladder junction, and any Accessory Ducts.
 
Secondary Endpoints:
 
1. The DR for students/residents only (apart from experienced surgeons), both before and after dissection.2. Time to Clip3. Incidence of Conversion to Open Surgery4. Volume of Bleeding5. Incidence of Bile Leakage from the liver bed6. Incidence of Bile Duct Injury (BDI)7. Surgeon Confidence Level 
Test Device/Procedure:
 
Image1 SPIES (Storz Professional Image Enhancement System) Endoscopic ICG Imaging System
 
Comparator Device/Procedure:
 
Standard Image1 SPIES Endoscopic System using white light imaging (WLI) only
 
Statistical Analysis:
 
The DR (before and after dissection) between arms will be compared using the chi-square test while the number of

--	--

structures detected will be analyzed using non-parametric tests. Regression models (logistic or generalized mixed models) will be fitted to evaluate if the effect of NIFC on the primary outcomes is modified by the patient's or surgeon's characteristics or the site.

2. Introduction

a. Background

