3. After removing the fat from the gallbladder area, lifting the gallbladder over the liver, and grabbing the Hartman's pouch to visualize the Calot's triangle, but PRIOR TO DISSECTION, the Researcher will use NIFC to determine what extra-hepatic biliary structures can be specifically identified. This involves toggling the light source back and forth between STD mode (WLI) and ICG mode (NIFC). Of note: because one of the goals of the Study is to evaluate NIFC as a teaching tool, residents and juniors should record what structures they were able to identify by themselves before any intervention of the attendant surgeon.
4. Then, AFTER DISSECTION, a similar assessment of what extra-hepatic biliary structures can be specifically identified using NIFC will be performed.
5. Anatomic anomalies of the biliary system will be documented on the case form and if an anatomic variation is found, a snap shot photo will be taken in addition to the video.
6. Immediately before clipping or proceeding with open surgery, the total time from Step 1 will be recorded, known herein as the "Time to Clip";
7. Before leaving the operation room, all participant surgeons and observers will complete the Intra-Operative Case Report Form (Appendices D and E, respectively).

d. Post-Operative Case Report Form

During the standard follow-up exam, typically 7-10 day post-op, the Researcher will complete the Post-Operative Case Report Form (Appendix F).

e. Bile Duct Injury Form (if needed)

If the procedure results in a bile duct injury, the operating surgeon will complete the ancillary Bile Duct Injury Form (Appendix G).

13. Statistical Plan

a. Sample size

We estimate that the six participant centers will be able to enroll a minimum of 1000 patients in a 12 months period. Table XX shows the minimum effect size (increase in the rate of detection) that we will be able to detect with a 90% power or more, 5% level of significance, one-side test, when the detection rate in the control group are the ones indicated in the first column.

Structure	Before dissection		After dissection	
	DR control group	DR increase (effect size)	DR control group	DR increase (effect size)
Cystic	50%	10%	100%	--
Right Hepatic Duct	40%	10%	80%	7%
Common Hepatic Duct	46%	10%	70%	8%
Common Bile Duct	46%	10%	96%	3%
Cystic-CBD junction	29%	9%	60%	9%
Cystic-Gallbladder junction	60%	9%	70%	8%
Accessory Ducts	1%	3%	2%	4%

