Regarding the main secondary outcome, incidence of injuries, the power to detect a drop from 8/1000 in the control arm to 2/1000 in the intervention arm, with a sample size of 500 patients per arm is 15%. Regretfully, with an achievable sample size as the one proposed above, the study will not have enough power to detect a drop in the incidence as important as the one considered.

b. Data Analysis

In general, descriptive statistics including frequencies and means will be used to characterize patient's baseline characteristics in both study arms. Analyses are designed to test the following hypotheses based on the primary objectives: Compared to those in the control arm, surgeons using NIFC will be able to identify a) more frequently the gallbladder cystic union (both before dissection and before clipping); b) a larger number of hepato-biliary structures and; c) more frequently some of the five hepato-biliary structures. We will test the first hypothesis using the chi-square test, the second one using non-parametric test (e.g. Kruskal-Wallis) and the third one using generalized mixed or hierarchical models to account for the clustering induced by the patient.

Multi-center Study Protocol: Efficacy of Near Infrared Incisionless Fluorescent Cholangiography (NIFC) during Laparoscopic Cholecystectomy

Regression models (logistic or generalized mixed models) will be fitted including covariates to evaluate if the effect of NIFC on the primary outcomes is modified by the patient's or surgeon's characteristics and site.

Regarding secondary outcomes we will use the Fisher's exact test or Chi square test (as needed) to compare proportion of patients with bile duct injury, open surgery or bleeding. Time to clipping and time to end of surgery will be compared between arms using the Kruskal-Wallis' test. Regression models will be used when possible -we expect very low incidence of injuries and open surgeries- to evaluate patient's and surgeon's effect modification.

Finally, for those outcomes specific for the NIFC group we will use logistic or generalized linear models to assess whether the reported helpfulness of the NIR light or the reflux maneuver is associated to patient's characteristics or surgeon's experience.

All statistical analysis will be conducted in R software.

14. Anticipated Problems and Solutions

a. Lower than expected Enrollment

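### 13.a sizes the detection-rate table for a one-sided 5% test, but the chi-square test in 13.b and the Summary has no alpha or one-sided rule; run two-sided, the stated 90% power is not reached

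*Combined protocol and SAP*

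**What the plan says.** Section 13.a takes its total from expected recruitment: the centers "will be able to enroll a minimum of 1000 patients in a 12 months period". It then tabulates, for each structure before and after dissection, the smallest rise over the control detection rate that can be detected with "90% power or more, 5% level of significance, one-side test". This is the only place in the document that gives an alpha or a sidedness.

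The tests are named elsewhere. The Summary (Statistical Analysis) says: "The DR (before and after dissection) between arms will be compared using the chi-square test". In 13.b, the first hypothesis is that surgeons using NIFC will identify "more frequently the gallbladder cystic union (both before dissection and before clipping", and the plan adds: "We will test the first hypothesis using the chi-square test". Neither place gives a significance level, a rejection region or a directional form of the test.

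The aim itself is directional. The primary objective is to "Demonstrate that NIFC performs better than standard white light (WLI) alone", and the 13.b hypotheses are phrased in terms of more frequent identification or more structures.

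**The concern.** A chi-square statistic on a 2×2 table squares the difference between arms, so in its usual form it rejects in either direction. At a nominal 5% it puts 2.5% in favor of NIFC, where the sizing assumed 5%. An analyst working from 13.b or the Summary could therefore run a test that does not deliver the power claimed in 13.a.

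Two things depend on the answer. One is whether the 90% claim holds. The other is whether the false-positive risk in favor of NIFC is 5% or 2.5% per comparison. In a narrow range of results the choice also decides significance, and the plan does not settle that choice before the data are seen.

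**Working it through.** **Inputs.** 500 per arm (stated in 13.a for the injury calculation; it also follows from 1,000 patients and the 1:1 allocation in 8.d). Control rates and increases come from the 13.a table. The cystic duct after dissection has a 100% control rate and no increase, which leaves 13 rows. No loss of primary data is assumed, in line with 14.b.

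**Formula** (pooled-variance normal approximation, no continuity correction). With d = p2 − p1 and p̄ = (p1 + p2)/2:

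SE0 = √[2p̄(1 − p̄)/n], SE1 = √{[p1(1 − p1) + p2(1 − p2)]/n}, power = Φ[(d − z·SE0)/SE1], with z = 1.645 one-sided or 1.960 two-sided.

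**Cystic-gallbladder junction, before dissection (60% to 69%).** SE0 = 0.03026, SE1 = 0.03013.
- One-sided: (0.09 − 1.645 × 0.03026)/0.03013 = 1.335, power 90.9%.
- Two-sided: (0.09 − 1.960 × 0.03026)/0.03013 = 1.018, power 84.6%.

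**After dissection (70% to 78%).** SE0 = 0.02774, SE1 = 0.02763.
- One-sided: 1.244, power 89.3%.
- Two-sided: 0.928, power 82.3%.

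The risk of missing the tabled gain thus goes from 9.1% to 15.4% before dissection, and from 10.7% to 17.7% after.

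**All rows.** Minimum increases are those giving 90% power by the same formula.

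| Row | Control, printed increase | Power 1-sided | Power 2-sided | Min. increase 1-sided | Min. increase 2-sided |
|---|---|---|---|---|---|
| Cystic, before | 50%, 10 | 93.8% | 89.0% | 9.20 | 10.18 |
| Right hepatic, before | 40%, 10 | 93.8% | 89.0% | 9.18 | 10.18 |
| Common hepatic, before | 46%, 10 | 93.6% | 88.7% | 9.24 | 10.23 |
| Common bile, before | 46%, 10 | 93.6% | 88.7% | 9.24 | 10.23 |
| Cystic-CBD, before | 29%, 9 | 91.6% | 85.5% | 8.71 | 9.68 |
| Cystic-gallbladder, before | 60%, 9 | 90.9% | 84.6% | 8.84 | 9.77 |
| Accessory, before | 1%, 3 | 91.9% | 86.1% | 2.84 | 3.28 |
| Right hepatic, after | 80%, 7 | 91.0% | 84.8% | 6.87 | 7.54 |
| Common hepatic, after | 70%, 8 | 89.3% | 82.3% | 8.10 | 8.92 |
| Common bile, after | 96%, 3 | 91.9% | 86.1% | 2.91 | 3.15 |
| Cystic-CBD, after | 60%, 9 | 90.9% | 84.6% | 8.84 | 9.77 |
| Cystic-gallbladder, after | 70%, 8 | 89.3% | 82.3% | 8.10 | 8.92 |
| Accessory, after | 2%, 4 | 94.4% | 89.9% | 3.51 | 4.01 |

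The one-sided column reproduces the plan. The printed increases are the one-sided minima rounded up, except in the two 70% rows, where 8.10 is printed as 8 and power is just short at 89.3%.

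**Sensitivity to method.** Exact binomial enumeration of the uncorrected two-sided chi-square gives 82.4% to 91.4% over the 13 rows; only accessory ducts after dissection exceeds 90%. The cystic-gallbladder junction has 84.7% and 82.4%. With continuity correction, on which 13.b is silent, exact two-sided power is 80.5% to 88.7%, and 83.1% and 80.5% for that junction.

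**Results that would split the two readings** (uncorrected):
- 350/500 control against 374 to 377/500 NIFC: one-sided p 0.045 to 0.028, two-sided p 0.090 to 0.055.
- 300/500 against 326 to 329/500: one-sided p 0.045 to 0.029, two-sided p 0.089 to 0.058.

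With continuity correction these windows move up by one patient, to 375–378 and 327–330.

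**False-positive risk in favor of NIFC**, exact, at control rates of 60% and 70%: 5.0% one-sided and 2.5% two-sided.

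**The case against.** The best reply is that 13.a and 13.b are two halves of one statistical plan. The only stated level is one-sided 5%, the objective and hypotheses are directional, and nowhere does the document say two-sided. A 2×2 chi-square is the square of a z statistic, so naming it does not exclude a one-sided rule. On this view the plan omits a sentence and does not contradict itself. Much of that stands: a one-sided intention is plausible, and the lower powers rest on a reading that the plan does not state. But a sizing assumption is not a rejection rule, and directional aims are often tested two-sided. The sections that an analyst would follow leave the rule open.

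It is also fair that the effect is modest. Power stays above 80% in every row even with continuity correction, and each window of conflicting results is four patients wide.

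Three stronger inferences are tempting and should not be drawn:
- That the table is miscalculated. It reproduces at one-sided 5%, apart from the slight shortfall in the two 70% rows.
- That the plan commits to a two-sided test and is therefore underpowered. No section says so.
- That 13.a itself mixes sidedness, because it gives 15% power for a fall in injuries from 8/1000 to 2/1000. A two-sided continuity-corrected normal formula gives 14.4%, but exact enumeration gives 38% or 18% one-sided and 25% or 10% two-sided (uncorrected or corrected). The plan names no method, so the 15% cannot identify sidedness.

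**Conclusion.** The mismatch is real and limited. The sizing assumes a one-sided 5% test, and the named test has no matching rule. If it is run in its usual two-sided 5% form, the 90% claim fails in all 13 rows by the pooled formula (12 of 13 by uncorrected exact enumeration). The loss is about 6 to 7 percentage points of power for the cystic-gallbladder junction. In terms of detectable increase it is about one point: 8.8 to 9.8 before dissection and 8.1 to 8.9 after.

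This rests on 500 analyzed patients per arm and on the control rates in the 13.a table. The particular windows of conflicting results also depend on whether a continuity correction is used. The documents do not show which sidedness was intended, so the finding is that the sections must be reconciled, and not that either is wrong. It is worth correcting because it concerns the decision rule for the primary endpoint and costs little.

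**What to change.** State the same sidedness and alpha for the primary test in 13.a, 13.b and the Summary, and say whether a continuity correction applies.

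- **If two-sided 5%:** either keep the printed increases and restate the power as at least 82% (at least 80% with continuity correction), or recompute every row by the table's own round-up rule. Under the pooled formula the second route raises all 13 rows by one point, to 11, 11, 11, 11, 10, 10 and 4 before dissection and 8, 9, 4, 10, 9 and 5 after, in table order. Common bile duct after dissection would then need 96% + 4 = 100%, so restating the power is the simpler route. Rounding to the nearest point should not be used: accessory ducts before and common bile duct after would keep their printed increases at 86.1% pooled power, against a 90% criterion.
- **If one-sided 5%:** say so in 13.b and the Summary, name a directional test (for example a signed z statistic, rejecting above 1.645), and note that the false-positive risk in favor of NIFC is 5% per comparison.

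The cost is wording, plus one restated power figure or a recomputed table. The 1,000 patients come from expected enrolment, so none need be added.

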Cost effectiveness of the technique was validated by Dip et al (35) with a total of 43 patients (21 males and 22 females). Mean age was 49.53 ± 14.35 years old and mean body mass index was 28.35 ± 8 kg/m² (2). Overall mean operative time was 64.95 ± 17.43 min. NIFC was faster than IOC (0.71 ± 0.26 vs. 7.15 ± 3.76 min; $p < 0.0001$). NIFC was successfully performed in 43 of 43 cases (100%) and intraoperative cholangiography (IOC) in 40 of 43 cases (93.02%) while in 3 patients IOC was not possible. NIFC was less expensive than IOC (US\$14.10 \pm 4.31 vs. US\$778.43 \pm 0.40; $p < 0.0001$). All surgeons found routine use of NIFC useful. Identification rates of extra-hepatic bile duct using NIFC ranges between 71 and 100 % depending on the study (32,33,34,35).

Osayi et al (36) studied eighty-two patients that underwent elective laparoscopic cholecystectomy and compared the use and utility of near infrared

Multi-center Study Protocol: Efficacy of Near Infrared Incisionless Fluorescent Cholangiography (NIFC) during Laparoscopic Cholecystectomy

incisionless fluorescent cholangiography (NIFC) vs intraoperative cholangiography (IOC). Mean age and body mass index (BMI) of the patients were 42.6 ± 13.7 years and 31.5 ± 8.2 kg/m², respectively. Indocyanine green was administered 73.8 ± 26.4 min prior to incision. NIFC was significantly faster to complete than IOC (1.9 ± 1.7 vs. 11.8 ± 5.3 min, $p < 0.001$). IOC was unobtainable in 20 (24.4 %) patients while NIFC did not visualize biliary structures in four (4.9 %) patients. After complete dissection, the rates of visualization of the cystic duct, common bile duct, and common hepatic duct using NIFC were 95.1, 76.8, and 69.5 %, respectively, compared to 72.0, 75.6, and 74.3 % for IOC. In 20 patients where IOC could not be obtained, NIFC successfully identified biliary structures in 80 % of the cases. (39)

Spinoglio et al (40) reported 45 cases between July 2011 and January 2012 with NIFC. The rates of visualization were 93 % for the cystic duct, 88 % for the common hepatic duct, and 91 % for the common bile duct prior to Calot's dissection; after Calot's dissection, the rates were 97 % for all three ducts. Mean hospital stay was 1.1 days and there were no bile duct injuries or any other major complications. (40)

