3. Compare the mean number of procedures that required Conversion to Open using NIFC vs WLI alone.
4. Compare the mean Volume of Bleeding using NIFC vs WLI alone.
5. Compare the Incidence rate of Bile Leakage from the liver bed using NIFC vs WLI alone.
6. Compare the Incidence rate of Bile Duct Injury (BDI) using NIFC vs WLI alone.
7. Compare the mean Surgeon Confidence Level using NIFC vs WLI alone.

5. Study Endpoints

a. Primary Endpoint:

Detection Rate (DR) of each particular extra-hepatobiliary structure during Laparoscopic Cholecystectomy (LC) defined as the total number of patients in which the particular structure is detected before and after dissection in that arm of the Study (WLI or NIFC), divided by the total number of patients in that arm. Extra-hepatobiliary structures to be included in this assessment: Cystic Duct, Right Hepatic Duct, Common Hepatic Duct, Common Bile Duct, Cystic-CBD junction, Cystic-Gallbladder junction, and any Accessory Ducts.

b. Secondary Endpoints:

1. The DR for students/residents only (apart from experienced surgeons), both before and after dissection.
2. Time to Clip
3. Incidence of Conversion to Open Surgery
4. Volume of Bleeding
5. Incidence of Bile Leakage from the liver bed
6. The mean Incidence of Bile Duct Injury (BDI)
7. Surgeon Confidence Level

6. Covariates

Besides the comparison of the outcomes in both study arms, we will conduct an exploratory analysis to identify potential effect modifiers. The following baseline variables will be considered:

- 1) Patient data:
 - a) Age
 - b) Gender
 - c) BMI
- 2) Patient history/condition:
 - a) obesity
 - b) liver disease
 - c) lithiasis
 - d) surgery status (elective/urgent/emergent)
- 3) Intra-operative factors:
 - a) amount of fat covering cystic artery
 - b) amount of inflammation
 - c) presences of adhesions / scar tissue
- 4) Surgeon expertise (resident/attendant)

7. Additional Observations (NIFC group only)

a. “Reflux Maneuver”

According to previous publications, in some cases the Cystic Duct may not be seen with NIFC because the Cystic Duct may not contain ICG at the time of viewing. In those cases, a “reflux maneuver” [defined as using an atraumatic laparoscopic instrument to push on the Common Bile Duct in order to move more of the ICG from the Common Bile Duct through the Cystic Duct into the Gallbladder – thereby increasing visualization of the Cystic-Gallbladder junction] can be performed.

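### Fourteen primary detection rates with no success rule, testing order, multiplicity control or analysis sidedness leave single structures, mainly after dissection, open to over-claiming

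*Combined protocol and SAP*

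**What the plan says.** - **Endpoint (Summary and 5.a).** The primary endpoint is the "Detection Rate (DR) of each particular extra-hepatobiliary structure during Laparoscopic Cholecystectomy (LC", for seven named structures, before and after dissection.
- **Sizing (13.a).** The table treats each structure and time point separately, at "90% power or more, 5% level of significance, one-side test". Cystic duct after dissection has an assumed control rate of 100% and no effect size, so 13 of the 14 cells are sized.
- **Test (Summary, Statistical Analysis).** "The DR (before and after dissection) between arms will be compared using the chi-square test". No alpha or sidedness is given.
- **Hypotheses (13.b).** Three are listed under the primary objectives: (a) the gallbladder-cystic union at two time points, by chi-square; (b) "a larger number of hepato-biliary structures", by a rank test, with no time point named; (c) "more frequently some of the five hepato-biliary structures", by "generalized mixed or hierarchical models to account for the clustering induced by the patient". The endpoint, the table and the surgeon and observer forms (Appendices D and E) all have seven structures, not five.
- **Cited after-dissection rates for NIFC (2.b).** The 82-patient series, listing the cystic duct first, reports that rates for the cystic duct, "common bile duct, and common hepatic duct using NIFC were 95.1, 76.8, and 69.5 %, respectively". In the 45-case series, "the rates were 97 % for all three ducts".

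No section says how many comparisons must succeed, in what order they are tested, or how alpha is shared. In 13.b the words first, second and third only match each hypothesis to its test.

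**The concern.** What counts as success, and at what error rate, can be settled after the data are seen. The plan also leaves open whether the mixed model for (c) gives one arm test or a test per structure, while the Summary plans chi-square tests on the detection rates.

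An endpoint defined for each structure invites claims about each structure. The exposure is greatest after dissection. There the assumed control rates are already high (96% for the common bile duct, 70% for the common hepatic duct) and the cited NIFC rates disagree: 76.8% and 69.5% in one series, 97% for both in the other. Those figures inform only two of the six testable after-dissection cells. They also need not equal this trial's NIFC arm, because the after-dissection step of the surgeon form lets that arm toggle between white light and ICG mode. Benefit after dissection is therefore uncertain, yet six such cells are each sized for an unadjusted test.

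**Working it through.** **Inputs.** 500 per arm (13.a); 13 control rates and increases from the table in 13.a; 5% one-sided (13.a only). The within-patient correlation is not given, so a latent correlation ρ from 0 to 0.9 is assumed.

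**1. Reproduce the table.** With control rate p, NIFC rate q = p + d and mean rate m = (p + q)/2:

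power = Φ{[d − z·√(2m(1−m)/500)] / √([p(1−p) + q(1−q)]/500)}

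For 70% to 78%: m = 0.74, the pooled SE is 0.02774 and the unpooled SE is 0.02763. At z = 1.645, power = Φ[(0.08 − 0.0456)/0.02763] = Φ(1.24) = 0.893. Over the 13 cells power is 89.3-94.4% at one-sided 5% and 82.3-89.9% at two-sided 5%. The table is thus one-sided, at the full 5% per cell, with no adjustment.

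The 15% power for bile duct injury in 13.a follows another convention. A two-sided continuity-corrected test gives 14.4%; the table's method gives 38.2%. Sidedness is therefore unsettled within 13.a itself.

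**2. Gains before dissection only.** Each patient has latent values √ρ·u + √(1−ρ)·v for the 13 cells, cut at the table's rates. The seven pre-dissection cells carry the tabulated increases and the six after-dissection cells have no effect. Pooled z-tests, 4,000 trials per setting (Monte Carlo SE about √(0.2 × 0.8/4000) = 0.6 points). Chance of at least one false after-dissection claim:

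| ρ | one-sided 5% | two-sided 5%, NIFC-favouring | Holm over 14, one-sided | Holm over 14, two-sided |
|---|---|---|---|---|
| 0 | 26.1% | 14.0% | 3.8% | 1.9% |
| 0.5 | 22.7% | 13.0% | 4.2% | 2.0% |
| 0.9 | 19.8% | 10.9% | 3.9% | 2.1% |

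Check at independence: 1 − 0.95⁶ = 26.5%; 1 − 0.975⁶ = 14.1%.

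**3. No effect anywhere, any one cell counts.** At independence, 1 − 0.95¹³ = 48.7% and 1 − 0.975¹³ = 28.0%. Simulated over ρ = 0, 0.5, 0.9 (8,000 trials): 49.4%, 38.3%, 30.2% one-sided; 27.9%, 21.8%, 17.2% two-sided, NIFC-favouring. A latent ρ of 0.9 gives a mean correlation between test statistics of only 0.42. If the statistics themselves correlated at 0.9, the rates would be 12% and 7%.

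**4. Milder readings, also with no effect anywhere and any one success counting.**
- Detection required at both times, so seven comparisons: 1 − 0.95⁷ = 30.2%; 1 − 0.975⁷ = 16.2% (independent).
- Section 13.b as three or four tests in all: 1 − 0.95³ = 14.3% and 1 − 0.95⁴ = 18.5% one-sided; 7.3% and 9.6% two-sided.

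**5. Cost of Holm over 14 hypotheses.** The strictest step uses 0.05/14 = 0.00357. For 70% to 78%, z = 2.690 one-sided gives Φ[(0.08 − 0.0746)/0.02763] = 0.577. Over the 13 cells:

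| | one-sided | two-sided |
|---|---|---|
| Unadjusted power at tabulated increases | 89-94% | 82-90% |
| Strictest Holm step | 58-71% | 49-62% |
| Simulated Holm power per cell, all 13 increases real | 76-87% | 63-78% |
| Same, seven pre-dissection cells, only those real | 67-75% | 57-67% |

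At control rates of 29-60%, the increase detectable with 90% power at the strictest step is 11.9-12.5 points one-sided (12.5-13.2 two-sided), against about 9 unadjusted one-sided. At 70% control it is 10.8 (11.4), against 8.1.

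**The case against.** The strongest reply is that the dramatic error rates need a rule that the plan never states. A reader might infer from the word some in hypothesis (c) that any single significant cell would be declared a success, and so that the trial carries a 30-49% false-positive rate. The documents do not support that as a description of the plan. The word permits the reading without setting the rule, and the figure also needs NIFC to improve nothing. Section 13.b, the more specific text, can be read as only three or four tests, and chi-square and Kruskal-Wallis tests are ordinarily two-sided. All of that stands, and it is why the pre-dissection-only scenario is the main figure here.

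A second reply is that NIFC's effects are so large that adjustment is academic. The 45-case series reports 93%, 88% and 91% before dissection, against assumed controls of 50%, 46% and 46%. Power at those rates stays about 100% even at the strictest Holm step. But they cover three of seven structures, and reference 40 identifies the series as single-site robotic cholecystectomy. The reply does not help after dissection: the common hepatic duct at 97% against 70% would survive, but the common bile duct at 97% against 96% has power of only 22% unadjusted one-sided and 3% at 0.05/14.

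Third, the correlation is assumed. That is true, and it moves the main figure only from 26% to 20% one-sided.

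**Conclusion.** The gap holds on the text alone: 14 primary cells, 13 of them sized at an unadjusted one-sided 5%, three loosely matching hypotheses, and no success rule, order, adjustment, analysis alpha or sidedness.

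Its practical size is a 20-26% chance (one-sided 5%) or 11-14% chance (two-sided 5%, NIFC-favouring) of at least one false after-dissection claim. This assumes that gains are real only before dissection, 500 per arm, the table's control rates, and ρ between 0.9 and 0. The 30-49% and 17-28% figures are conditional on an any-cell rule and no benefit at all, and should be quoted only with those conditions.

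A reader might also infer that the trial's main finding is at risk. The documents do not show that: the cited pre-dissection effects, for the three structures they cover, would survive adjustment. This should be fixed before the arms are compared. It is not a reason to doubt the design.

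**What to change.** In 13.b:
- Name the seven structures as in 5.a.
- State alpha and sidedness once. Two-sided 5% matches the chi-square and Kruskal-Wallis tests named.
- Report cystic duct after dissection descriptively.
- Test (b) before dissection.
- Take the structure-by-time contrasts from one named analysis, either the mixed model or chi-square tests, and align the Summary.
- Apply Holm over the 13 detection rates plus (b), 14 hypotheses; (a) is covered by its two cells.
- Limit the primary claim to the comparisons that survive.

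In 13.a, label the table as unadjusted one-sided 5% per cell, and add the Holm power and detectable increases from step 5. Otherwise its claim of at least 90% power conflicts with 13.b.

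A fixed sequence in the order (a), (b), (c) is less attractive. Everything would depend on the cystic-gallbladder junction improving at both times. At the tabulated increases that gate passes 0.909 × 0.893 = 81% of the time one-sided (0.846 × 0.823 = 70% two-sided) if the two times are independent, and somewhat more often if they are positively correlated. With no after-dissection gain it passes at most 5% of the time. A sequence that starts before dissection would avoid this and is a possible alternative, if it is written down beforehand.

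The cost is SAP wording, a few lines of R, a revised table and lower stated power at the tabulated minimum increases. No new patients or data are needed.
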